## 2) Draw inferences regarding the effect of key factors on patient outcome

Before any modelling work is undertaken, we will do a thorough descriptive analysis of the datasets and look for potential issues that would need to be addressed at an early stage, such as a large proportion of missing data for key confounders or an unusual distribution of age/weight/diagnosis or other risk factors. Prior to multivariate modelling, we will explore univariate associations between key explanatory variables (timeliness, care delivered) and potential confounders with our stated primary and secondary outcomes. All explanatory variables and confounders with significant univariate association with outcome will be considered in the regression modelling for Models 1 and 2. We will develop statistical models to study the association between timeliness of access to intensive care and clinical outcomes, and the association between care delivered by PIC retrieval teams and clinical outcomes. Since we recognise that the data could potentially be clustered by PICRT, we will develop multilevel models as appropriate (to include the random effects of PICU/PICRT/general hospital) depending on the outcome:

- Mortality at fixed time-points: logistic regression
- Length of stay (PICU, hospital), resource use in PICU and hospital resource use following
   PICU discharge: linear, Poisson or negative binomial regression models (as appropriate) and survival models
- A&E attendances: Poisson or negative binomial regression model (as appropriate)

For both Model 1 and Model 2, several multivariate models will be developed and Akaike Information Criterion (AIC) used for further model selection. We will also use cross-validation methods alongside an examination of model residuals and leverage, to ensure we are not overfitting. Different models will contain different combinations of the potential confounders, which will be chosen from a set. We will also include other risk factors within the models, including patient- and organisation-level factors (but not limited to): patient age, weight, ethnicity, index of multiple deprivation, co-morbidities, geographical region, distance from PICRT base to referring hospital, distance from referring hospital to admitting PICU, season (summer: Mar-Aug vs. winter: Sep-Feb) and bed occupancy of the nearest PICU. For each model, we will carefully consider the inclusion/exclusion of confounders that could mask the effect of timeliness (e.g. distances; PIM-2 score) or team composition (geographical region, if this is a key determinant of team composition).

We will also analyse the data using propensity scores – this technique will help us to include a large number of confounders in the analysis.

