Based on the clinical knowledge generated through the above process, we will produce directed acyclical graphs (DAG) to visually examine the assumptions regarding the causal structure of the variables being analysed and to help decide which variables should be included as confounders. The visualization of the process will also help in the identification of measurable factors that might serve to block a backdoor path including an unmeasured (or unmeasurable) confounder. It will also serve to allow the effect of any likely bias induced by unmeasured confounding to be estimated. DAGs will also help differentiate confounding variables (variables that affect the outcome and have an association with the exposure status) from variables that could potentially be used as instruments in the instrumental variable analysis (variables that affect the exposure status but not the outcome, other than through the exposure). The final DAG will be derived by consensus where possible, or by a majority view of the experts involved if necessary.

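### A crude-significance filter and AIC choose covariates alongside the DAG with no stated order of precedence; the DAG should fix the adjustment set and the exposure should always stay in

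*Protocol*

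**What the plan says.** Three selection rules stand in Protocol section 8.1.3.4.

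- **DAG (step 1).** After clinical input, "we will produce directed acyclical graphs (DAG) to visually examine the assumptions regarding the causal structure of the variables being analysed". Covariate choice is a stated purpose of these graphs: they are meant "to help decide which variables should be included as confounders".
- **Univariate screen (step 2).** Before multivariable modelling, "we will explore univariate associations between key explanatory variables (timeliness, care delivered) and potential confounders with our stated primary and secondary outcomes". The next sentence is the filter: "All explanatory variables and confounders with significant univariate association with outcome will be considered in the regression modelling for Models 1 and 2". No p-value threshold is given.
- **AIC (step 2).** For both models, "several multivariate models will be developed and Akaike Information Criterion (AIC) used for further model selection". What varies between candidates is stated: "Different models will contain different combinations of the potential confounders, which will be chosen from a set".

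Other text in the same section bears on how strictly these rules apply. Straight after the filter comes a commitment with no condition attached: "We will develop statistical models to study the association between timeliness of access to intensive care and clinical outcomes". Step 1 includes time at the general hospital and adult intensive care as confounders, and step 2 adds a list of patient and organisational risk factors; neither inclusion depends on significance. On variables such as distance and PIM-2, "we will carefully consider the inclusion/exclusion of confounders that could mask the effect of timeliness". Propensity scores are also planned. No sentence ranks the DAG, the screen and AIC.

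**The concern.** The aim of Models 1 and 2 is to estimate the effect of delay and of team care on outcome. Whether a variable is a confounder depends on the causal structure, which is the reason for drawing a DAG. A crude p-value does not measure that, and it fails where confounding runs against the effect. If sicker children are reached sooner, severity pulls the crude association between delay and death towards the null or past it.

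AIC rewards fit to the outcome, so it can discard a variable strongly tied to delay but only modestly tied to death. Intervals computed as if the selected model had been fixed in advance can also be too narrow, although no figure is put on that here.

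The estimates concern the primary outcome, 30-day mortality. They also inform the service modelling in section 8.4, and section 8.4.6 contemplates a causal reading of them.

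**Working it through.** **The plan's own figure.** Section 8.1.3.5 gives 7% mortality, 85% reached within 3 hours, a 3-point difference, 80% power, alpha 5% and a minimum of 9,685 transports after an unstated clustering allowance. For 7% against 10%, two-sided, with allocation ratio k = 15/85 and pooled p = 0.85 × 0.07 + 0.15 × 0.10 = 0.0745:

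- n(<3 h) = [1.96 √(0.0745 × 0.9255 × (1 + 1/k)) + 0.8416 √(0.07 × 0.93 + 0.10 × 0.90/k)]² / 0.03² ≈ 4,299
- total = 4,299 × (1 + k), about 5,059 after rounding up
- implied design effect = 9,685/5,059 ≈ 1.91, an intracluster correlation of about 0.001 with 10 equal teams

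The figure is plausible but cannot be confirmed, because the allowance is not given. It supplies the inputs below.

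**Masking of the exposure: assumptions.** From the plan: N = 15,000, 7% mortality, 15% delayed, and OR = (0.10/0.90)/(0.07/0.93) = 1.476. Not in the documents: 30% severe, severity OR 4 for death, 8% of severe and 18% of other children delayed (0.3 × 0.08 + 0.7 × 0.18 = 0.15), and a two-sided 5% threshold. The logistic intercept is solved for 7% overall mortality.

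| Group | Share | Mortality |
|---|---|---|
| Severe, delayed | 0.024 | 18.7% |
| Severe, not delayed | 0.276 | 13.5% |
| Other, delayed | 0.126 | 5.4% |
| Other, not delayed | 0.574 | 3.75% |

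- Crude mortality, delayed: (0.024 × 0.187 + 0.126 × 0.054)/0.15 ≈ 7.6%
- Crude mortality, not delayed: (0.276 × 0.135 + 0.574 × 0.0375)/0.85 ≈ 6.9%
- Crude OR = 1.10, log OR 0.097
- SE = √[1/(2,250 × 0.0755 × 0.9245) + 1/(12,750 × 0.0690 × 0.9310)] = 0.087, so z = 1.11
- P(crude p > 0.05) = Φ(1.96 − 1.11) − Φ(−1.96 − 1.11) ≈ 0.80. Dividing z by √1.915 for the design effect gives 0.87.
- Severity-adjusted: log 1.476 = 0.389, SE 0.090, z = 4.32, so the test misses in 1% of studies (12% with the design effect)

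**Sensitivity to the assumptions (N = 15,000, no design effect).**

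- Severity OR 3 to 5 and severe-child delay rate 6% to 10%, holding overall delay at 15%: P(crude p > 0.05) runs from 0.22 to 0.95.
- No severity-delay association: crude OR 1.46, significant in 99.6% of studies.
- Sicker children wait longer (22% against 12%): crude OR 1.85, significant almost always.
- Separate simulation (1,000 datasets per scenario, true delay OR 1.5, severity-death OR 4, no clustering): with severity-delay OR 0.7, 0.5 and 0.3, the adjusted effect was significant while the crude test was not in 10%, 48% and 90% of datasets.

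**Loss of a confounder.** In the illustration above, severity itself would pass any screen. So take instead a confounder with 30% prevalence and the same delay pattern that only just fails.

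- SE of its crude log OR ≈ √[1/(4,500 × 0.07 × 0.93) + 1/(10,500 × 0.07 × 0.93)] = 0.070
- The threshold crude OR is exp(1.96 × 0.070) ≈ 1.15
- Omitting such a variable moves the delay OR from 1.48 to about 1.43

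**The case against.** A reader might infer that timeliness must pass both the screen and AIC, that the screen overrides the DAG, and that the primary question could be closed at the crude stage. The documents do not support that.

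- The filter says significant variables will be considered; it does not say that others are excluded.
- The next sentence commits to timeliness models, and a Model 1 without timeliness would have no object.
- AIC is described for combinations of confounders, not for the exposure.
- Several covariates are included without any significance condition, and masking is expressly recognised.
- Nothing ranks the screen above the DAG. Propensity scores, instrumental variables and sensitivity analyses follow, and the analysis plan, not shown here, is to settle the confounding strategy before modelling starts.

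The 80% figure quantifies only loss of the exposure, under assumed inputs whose direction the protocol does not state. Losing one confounder that barely fails the screen costs little. Downstream reach is also limited: workstream C fits its own regressions comparing service models, and section 8.4.6 only explores whether a causal extension is possible.

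All of this stands as a limit on the point. It does not remove it. A significance filter has no function unless variables that fail it are treated differently, and its wording names the exposures. None of the safeguards is given priority over it. This is also not a detail left to the analysis plan: the protocol itself states the screen and AIC, so an analysis plan that follows it inherits the conflict.

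**Conclusion.** The point holds as a defect in stated method: a crude-significance filter, worded to include the exposures, and AIC choice of confounders stand beside a DAG with no order of precedence. For effect estimation the DAG should govern.

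The size is conditional. Under the assumed negative confounding, the crude OR is 1.10 against a true 1.48 and the crude test is non-significant in about 80% of studies (87% with the implied design effect), while the adjusted test misses in 1% (12%). Without a severity-delay association, or if sicker children wait longer, the filter would almost never discard delay. For a single confounder just below the threshold the shift is small, 1.48 to about 1.43. Several such variables, or a confounder whose own crude association is masked, could matter more, but the documents identify none. It should be fixed; it does not show that the primary analysis will fail.

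**What to change.** In section 8.1.3.4 step 2, and in the analysis plan:

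- Delete the univariate-significance rule; keep univariate results as description only.
- State that the exposure stays in every model.
- Let the DAG fix one primary adjustment set for each exposure, retained regardless of significance or AIC.
- Limit AIC and cross-validation to functional form, for example the shape of continuous covariates.
- Report other adjustment sets, including those with and without distance or PIM-2, as labelled sensitivity analyses.

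The cost is wording. A few weakly predictive covariates stay in the model, which about 15,000 × 0.07 = 1,050 expected deaths can support.

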#### 3) Investigating unmeasured confounding

We will primarily use instrumental variable analysis to study the effect of unmeasured confounding in this study. Identifying a suitable instrumental variable (IV) in this setting is likely to be challenging, since it needs to satisfy three key assumptions: a) the IV must not be correlated with patient outcome, except through the effect of the exposure; b) the IV must be highly predictive of the exposure; and c) the relationship between the IV and the exposure must not be confounded. Because the first assumption is empirically unverifiable, the choice of the instrument heavily relies on expert clinical knowledge – we will propose and discuss various candidate instruments at the PMGs and the first SSC meeting (months 4-6). The choice of the 'best' instrumental variable will be finalised as part of the analysis plan, based on clinical and statistical input. We anticipate that candidate IVs will include variables such as distance to the referring hospital (nearby hospital versus distant hospital) and activity level at the time of referral (based on number of other ongoing retrievals within the retrieval service at the time of referral). We will also use sensitivity analyses to estimate the effect of unmeasured confounding on our study findings.

## 8.1.3.5 Sample size calculations

PICANet data from 2014/15 indicates that the 30-day mortality rate for transported PICU admissions is approximately 7% and that PICRTs reach critically ill children within 3 hours of referral acceptance in 85% of cases. Accounting for the potential for clustering of data by PICRTs, we calculate that a minimum of 9685 transports would allow us to detect a 3% difference in 30-day mortality between the two groups (transports taking ≥3 hours to reach patient bedside and transports taking <3 hours to reach patient bedside) with 80% power and alpha 5%. We will analyse PICANet data from transported PICU admissions over a 3-year period (nearly 15,000 transports) to ensure adequate sample size for our analysis.

## 8.2 Workstream B: Qualitative and questionnaire study

This work stream will address the following two objectives of the DEPICT study: Objective 1.3: To explore parents', and where feasible children's, experiences of emergency transport to PICU, and

Objective 1.4: To explore clinicians' and service managers'/commissioners' perspectives of PICU transport and its impact on care provided to critically ill children and young people, and the wider impact on other patients and services.

We will employ a mixed-methods approach with a convergent triangulation study design whereby quantitative and qualitative data will be collected concurrently, with equal weight being given to both work streams. We will integrate findings from the qualitative and questionnaire study (how do national variations in the timeliness of access to emergency intensive care and care delivered by PICRTs affect patient/family experience?) with findings from the quantitative study (how clinical outcomes are affected by national variations) at the interpretation stage to generate complementary views of paediatric retrieval. Uniquely, the qualitative study will gather rich narrative detail from patient experiences and clinician perspectives that cannot be obtained from quantitative analyses of routine data.

See Appendix D for schedule of procedures involved in the qualitative and questionnaire study. See Appendix E for the data flow involved in the qualitative and questionnaire study.

## 8.2.1 RECRUITMENT OF TRANSPORTED CHILDREN AND THEIR PARENTS

Parents of all critically ill children and young people transported to one of the 24 participating PICUs in England and Wales during a 12-month period (and where feasible, the children/young people themselves) will be eligible for recruitment to the qualitative and questionnaire study. Transport may have been performed by PICRTs or, less commonly, by other transport teams.

Clinical staff at each participating PICU will screen for eligible participants at PICU admission. Participants (parents and children/young people) who meet the inclusion criterion will be approached by suitably qualified and trained clinical/research staff to discuss the study. Written informed consent will be sought from eligible participants: a) for completion of a questionnaire relating to the experience of PIC transport;

b) to be contacted by a qualitative researcher based at Great Ormond Street Hospital for potential participation in an interview at a later date;

c) to be contacted by the qualitative researcher for completion of quality of life questionnaires 12 months later; and

d) for the use of patient identifiers to extract data from PICANet relating to the individual child's transport episode.

A detailed study information sheet will be provided. Adequate time will be provided for parents and children/young people to consider taking part in the study. It is anticipated that the majority of children/young people will be too young and/or too ill to participate directly in the consent process; however, age-appropriate information sheets and assent forms will be used where appropriate.

## 8.2.1.1 Bereaved parents

It is possible that some children may unfortunately die before the clinical/research staff have the opportunity to discuss participation in the study with their parents. In this situation, we do not intend to exclude parents from participating in the research; excluding parents of children who die will also introduce selection bias into the study. Recognising that the standard consent processes will not be suitable for these situations, after consultation with parent co-applicants and the Study Steering Committee, we have developed a separate consent process for this subgroup of parents. We have also developed versions of the participant information sheet and consent forms for bereaved parents. Parents will be approached several weeks after the child's death (timing left to the discretion of the clinical team involved in the care of the child) by means of a personalised letter sent from the study Principal Investigator (PI) for the relevant research site. Enclosed with the personalised letter will be the appropriate participant information sheet, two self-complete consent forms and two copies of the transport questionnaires. Bereaved parents will be invited to participate in the study (to complete the transport questionnaire and agree to be contacted for participation in an interview, but not for the 12-month quality of life questionnaire). If the parents decide to participate in the study, they will be able to return the signed consent form(s) in a replypaid envelope. Completed transport questionnaires will be returned in a separate reply-paid envelope or completed online (see below).

## 8.2.2 QUESTIONNAIRE STUDY

Clinical/research staff at each participating PICU will give a paper questionnaire to parents who consent to completing a questionnaire relating to the experience of PIC transport. Based on our ongoing research experience of collecting long term follow up information from children transported by the CATS team (BASIC, NIHR portfolio ID 15920) we will also offer parents the option to complete this questionnaire electronically using a secure online system (only centre and study numbers will be used; no identifiable data will need to be entered into the questionnaire). Wherever possible and relevant, both parents will be offered the opportunity to complete the

transport questionnaire individually if they were present for some of their child's transport to intensive care, recognising that parents may have different perspectives and capturing both viewpoints would enrich the description of family experiences.

We recognise that some patients will be from families who do not speak/write English and that these families may generally have a poorer experience of health care. Therefore, we will discuss with different PICRTs, and arrange for the information leaflet, consent form and transport questionnaire to be translated into the 5 most commonly spoken languages (other than English).

We will develop the questionnaire from similar existing questionnaires and from relevant literature, and use the experience of the study team, the steering group and parent representatives to further inform its format and content before it is finalised.

The questionnaire will seek parental responses to specific questions regarding their experience during and after their child's transport to PICU. We will cover aspects such as how long they waited for a PICRT to arrive, what information was provided regarding the transport process, expectations of the transport and whether these were met, medical staff involved from the PICRT, whether parents were able to accompany their child in the ambulance, duration and experiences of the journey and handover on arrival at the PICU, and whether they felt informed and involved in their child's care. We will use a mixture of rating scales, tick box questions and free text boxes; the questionnaire will be designed to take no longer than 15 minutes to complete. We will pilot the questionnaire first to ensure that it is acceptable to parents. Parents will be given a reply-paid envelope to return the questionnaire directly to the study team or, if they prefer, they will be able to return the questionnaire to a study collection box on the PICU.

Since postal response rates to questionnaires are typically about 20-25%, we anticipate receiving 800-1000 completed questionnaires (around 4500-5000 critically ill children are transported to PICU by PICRTs each year). We will link data from the questionnaires with PICANet audit data collected for that particular transport to provide additional information for the analysis (e.g. time to arrive at bedside).

## 8.2.3 PARENT INTERVIEWS

#### 8.2.3.1 Sampling

We aim to recruit approximately 5 parents of children/young people transported by each of the 10 PICRTs across England and Wales for participation in an interview (total of approximately 50 interviews). This number will be sufficiently large to enable us to capture the range of parents' experiences across the different models of care and to reach data saturation, whilst being mindful of the resource implications and feasibility of collecting and analysing large amounts of interview data within the project time-frame. We will select eligible participants from the cohort of parents who have consented for the interview, using sampling criteria as below:

- Patient age: infant (<1 year), young child (1-4 years), older child (5-12 years), teenager (13-16 years)

- Main diagnosis: severe infection, cardiac disease, trauma, neurological disease, other
- Pre-existing health condition: none, at least one pre-existing health condition
- Timeliness of access to intensive care: ≥3 hours, <3 hours from referral to PICRT arrival at patient bedside
- Patient's home location: rural, urban
- Whether the parent accompanied the child in the transport to the PICU (yes; no)

Across the PICRTs, this purposive sampling strategy will ensure diversity in terms of the child/young person's underlying condition, new/existing disease/injury, rural/urban location, distance to PICU and time taken for the PICRT to reach the patient bedside. Further, since we will have sampled from each of the PICRTs, there will be diversity in terms of the variations in care delivered by the PICRTs (team composition, interventions performed during transport). Finally, we will aim to ensure diversity in terms of ethnicity and socioeconomic status.

